### Permanent Discontinuation

A subject will permanently discontinue treatment with investigational product in the event of:

- Dose-limiting or other unmanageable toxicity. Exception: If a DLT occurs in a subject with a clear clinical benefit from treatment a restart at a lower dose and / or implementation of a dose step can be considered if the toxicity has resolved and after consultation with the sponsor
- Grade 4 CRS
- Grade 3 CRS occurring at the initial run-in dose for a cycle (ie, at the MTD1)
- Grade 2 or 3 CRS meeting any of the criteria listed below:
  - Grade 2 or 3 CRS that does not improve to  $\leq$  grade 1 within 7 days
  - Grade 3 CRS that does not improve to  $\leq$  grade 2 within 5 days
  - If a subject experiences 2 separate grade 3 CRS events
- Disease progression as defined by revised IWG response criteria ([Appendix E](#) for R/R AML, Section [7.6](#) for MRD+ AML and [Appendix K](#) for MDS).
- Withdrawal of subject's consent to treatment
- Subject or investigator not compliant with the study protocol
- Occurrence or progression of a medical condition which in the opinion of the investigator should preclude further participation of the subject in the study

- Hematological or extramedullary relapse subsequent to CR/CRh/CRi/morphologic leukemia-free state on protocol treatment for R/R AML. Exception: a blast count > 5% at the pre-dose assessment (after the infusion-free interval) would not lead to permanent treatment discontinuation even if the count had been < 5% directly after the previous treatment cycle.
- An infusion interruption of more than 21 days due to an adverse event not clearly related to the underlying disease.
- Occurrence of CNS-related adverse event considered related to AMG 330 by the investigator and meeting one or more of the following criteria:
  - More than one seizure
  - A CNS-related adverse event CTCAE Grade 4
  - A CNS-related adverse event leading to treatment interruption that needed more than one week to resolve to CTCAE Grade ≤ 1
- Non-manageable Graft versus host disease
- Investigator's decision that a change of therapy (including immediate HSCT) is in the subject's best interest
- Administration of relevant non-permitted concomitant medications

Women who become pregnant while on study through 1 week after receiving the last dose of study drug will not receive subsequent scheduled doses and will be followed for safety until the end of study visit.

Men with pregnant partners or whose partners become pregnant while the subject is on study will receive subsequent scheduled doses and must practice sexual abstinence or use a condom while on study through 12 weeks after receiving the last dose of study drug.

All reasons for treatment discontinuation should be clearly and concisely documented in the eCRF. If a subject has not continued to present for study visits, the investigator should determine the reason and circumstances as completely and accurately as possible.

In any case of premature treatment discontinuation, the investigator should make every effort to perform all examinations scheduled for the End of Treatment (EOT) and EOS visits. These data should be recorded, as they comprise an essential evaluation that should be performed prior to discharging any subject from the study and to allow for the evaluation of the study endpoints.

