### 7.2.3 End of Treatment

The EOT visit will occur upon documented confirmed disease progression, intolerable adverse event, or withdrawal of consent. See Section 6.2.1.5 for a complete list of reasons for permanent treatment discontinuation. For subjects who choose to discontinue investigational product treatment, the EOT visit should occur as soon as possible after the last dose of investigational product is administered. Medically significant adverse events, considered related to the investigational product by the investigator or the sponsor, will be followed until resolved or considered stable. The following procedures will be completed during the EOT visit as designated in the Schedules of Assessments (Table 8 – Table 23)

- Clinical evaluation
  - Physical examination as per standard of care. Physical examination findings should be recorded on the appropriate eCRF.
  - ECOG performance status
  - Weight
- Vital signs (ie, blood pressure, heart rate, respiratory rate, and temperature)
- Pulse oximetry

- Laboratory assessments: hematology, chemistry, coagulation, urinalysis
- Biomarker assessments: immune cell subsets and markers of immune system activation, plasma biomarkers
- Anti-AMG 330 antibody sample collection
- Serious adverse event reporting
- Adverse event reporting
- Disease-related event reporting
- Documentation of concomitant and rescue medications

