## **8.3           Reasons for Removal From Treatment or Study**

### **8.3.1       Reasons for Removal From Treatment**

Reasons for removal from protocol-required investigational product(s) include any of the following:

- Subject request
- Safety concern (eg, due to an adverse event, non-compliance, requirement for alternative therapy, or pregnancy)
- Death
- Lost to follow-up
- Confirmed disease progression as defined by revised IWG response criteria and ELN response criteria ([Appendix E](#), [Appendix K](#) and [Appendix M](#)) or disease progression accompanied by worsening of symptoms or deterioration of the subject's general condition
- Protocol specified criteria:

- Proceeding to HSCT

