### **Progressive Diseasea**

Progressive disease for patients with AML is defined as:

- Greater than 50% increase in bone marrow blasts from the best assessment and at least 20% marrow blasts.
- Greater than 50% increase in the peripheral blood absolute blast count and at least an absolute blast count of 1000/cmm.
- Development of extramedullary disease. If the patient has extramedullary disease at baseline, then the development of a new site of disease.
- In patients who present with a bone marrow blast percentage sufficiently high to preclude the ability to determine disease progression by a > 50% increase in the marrow blast percentage, then disease progression will be determined by peripheral blood criteria or the development of new sites of extramedullary disease.

a Patients may remain on study treatment if the investigator believes the patient is deriving some benefit.

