Duration of response is defined as the interval from the date of the first disease assessment indicating an overall response to the first documented relapse, disease progression, or death due to any cause, whichever occurs first. Subjects without relapse, disease progression or death until the analysis data cut-off date will be censored at the last adequate disease assessment date. Only subjects with a response will be evaluated for DOR.

DOR time in days = earlier of (date of first relapse or disease progression or death or date of censoring) – date of the first observation of overall response +1.

DOR time in months= earlier of (date of first relapse or disease progression or death or date of censoring) – (date of the first observation of overall response +1)/30.4

Overall Survival (OS)

Overall survival is defined as the time from enrollment until death due to any cause.

Subjects alive will be censored at the last known date. If the date last known to be alive is after the date that triggers the analysis (ie, the data cutoff date), the subject will be censored at the date of last contact through the analysis trigger date.

Event-free Survival:

Event-free survival (EFS) is defined as the interval from first administration of AMG 330 to the earliest of date of treatment failure, relapse for responders, or death due to any cause. Censoring is at the last evaluable post-baseline response assessment; otherwise,

at first administration of AMG330. For non-responders, the event date for treatment failure is assigned as the date of first administration of AMG 330.

Event-free Survival in days = earlier of (date of treatment failure or relapse or death or date of censoring) – date of the first administration of AMG 330 +1.

Event-free Survival in months = earlier of (date of treatment failure or relapse or death or date of censoring) – (date of the first administration of AMG 330 +1)/30.4.

Time to Response (TTR)

Time to response defined as the interval from the first administration of AMG 330 to the first documentation of response. Time to response is evaluated only for subjects who achieved a response.

Time to response is calculated as the number of days:

(date of first response – date of study day 1 +1).

6. Analysis Sets

The analysis of all endpoints, unless noted otherwise, will be conducted on the Safety analysis set defined in [Section 6.1](#).

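### For R/R AML, Section 6.2.1.5 makes progression a mandatory permanent stop, but its cited definition in Appendix E allows treatment to continue and Sections 7.2.3 and 8.3.1 refer to confirmed progression, so what happens after progression depends on the passage a site follows

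*Protocol*

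**What the plan says.** Protocol Section 6.2.1.5 (Permanent Discontinuation) opens with "A subject will permanently discontinue treatment with investigational product in the event of" and lists "Disease progression as defined by revised IWG response criteria", citing Appendix E for R/R AML. That bullet has no confirmation step and no exception. Other bullets in the same list do carry exceptions: the one on dose-limiting toxicity continues "Exception: If a DLT occurs in a subject with a clear clinical benefit from treatment a restart at a lower dose", and the one on relapse exempts certain pre-dose blast counts.

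Appendix E attaches a footnote to its heading on progressive disease: "Patients may remain on study treatment if the investigator believes the patient is deriving some benefit".

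Section 8.3.1 gives as a reason for removal from treatment "Confirmed disease progression as defined by revised IWG response criteria and ELN response criteria", or else "disease progression accompanied by worsening of symptoms or deterioration" of general condition.

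Section 7.2.3 says "The EOT visit will occur upon documented confirmed disease progression", then refers the reader to Section 6.2.1.5 for the full list of reasons for permanent discontinuation. In the other direction, the list of reasons for infusion interruption in Section 6.2.1.5 refers to Section 8.3 for discontinuation criteria.

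SAP Section 5.4 sets no cut-off at progression for overall response or time to response. It runs duration of response (DOR) from the first response "to the first documented relapse, disease progression, or death due to any cause, whichever occurs first". Its treatment-emergent window closes at the earlier of 30 days after last dose and end of study.

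**The concern.** For an R/R AML subject who meets the Appendix E criteria for progression but feels well, these passages give different instructions. Section 6.2.1.5 stops treatment. The footnote permits it to continue on the investigator's judgement of benefit. Sections 8.3.1 and 7.2.3 look for confirmation, or in 8.3.1 for clinical worsening. The decision is a practical one: Section 6.2.1.1 uses marrow results to decide between starting the next cycle and applying the permanent discontinuation criteria.

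At stake is comparability across about 17 sites. The same clinical course could be recorded as a one-cycle non-responder at one site and as a multi-cycle subject, possibly a responder, at another. Adverse event incidence is part of the primary endpoint, and the response rate informs the review of the first 10 expansion subjects.

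**Working it through.** No figure in the plan is in dispute, so the main check sets the passages side by side for one case: R/R AML, Appendix E progression at the end of cycle 1, no symptoms, no repeat assessment.

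- Section 6.2.1.5: stop. No exception applies to this bullet.
- Appendix E footnote: may continue if the investigator believes there is some benefit.
- Section 8.3.1: neither limb is met. Progression is not confirmed and there is no clinical worsening.
- Section 7.2.3: the end-of-treatment visit is not triggered by its own wording, but its cross-reference leads to 6.2.1.5, which says stop.

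No passage defines confirmation of progression. The repeat marrow in Appendix E concerns relapse with low blast percentages. The cross-references do not settle the order either, since 7.2.3 points to 6.2.1.5 and 6.2.1.5 points to 8.3.

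**Population.** Protocol Section 10.2 plans about 70 R/R AML subjects in Group 1 escalation, up to 30 in its expansion, and about 24 in Groups 4 and 5: 70 + 30 + 24 = 124 of 256. This is everyone to whom the conflict could apply, not the number expected to be affected.

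**Exposure and adverse events.** Protocol Section 3.5.1 allows up to 5 further cycles after cycle 1, so the case above has 0 further cycles under one reading and up to 5 under another. The treatment-emergent window and the end-of-study visit both run from the last dose, so they move with it.

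**Response.** With no cut-off at progression, a later remission counts. Event-free survival follows: SAP 5.4 dates a non-responder's failure at first dose, whereas a subject who responds late is classed as a responder with a later event date.

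**Review of the first 10 expansion subjects.** The plan's own figures reproduce. The probability of no response in 10 is (1 − p)^10:

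- p = 5%: 0.95^10 = 59.9% (plan: greater than 59%).
- p = 20%: 0.80^10 = 10.7% (plan: less than 11%).

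The documents give no rate of response after progression. As an assumption only, suppose treatment past progression added 2, 5 or 10 percentage points to a 5% rate and every such response was seen in time. The probability of at least one responder in 10 is 1 − (1 − p)^10:

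- p = 5%: 40.1%
- p = 7%: 51.6%
- p = 10%: 65.1%
- p = 15%: 80.3%

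This overstates the effect, because the review can take place once the tenth subject has completed cycle 1 plus two weeks. With a 28-day cycle that is 28 + 14 = 42 days, so late responses would come mainly from subjects enrolled earlier.

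**Full expansion cohort.** One extra late responder in 30, from 6 to 7, moves the rate from 20.0% to 23.3% and the exact 80% interval from 10.9–32.5% to 13.5–36.1%.

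**The case against.** The best defence is that the passages do not rank equally. Section 7.2.3 concerns a visit and defers to 6.2.1.5. Section 8.3.1 is a list of possible reasons, softer than a mandatory stop. Section 6.2.1.5 also sends the reader to Appendix E, so its footnote could be read as part of the rule, in line with the judged-benefit condition for further cycles in Section 3.5.1. This narrows the conflict but does not remove it. The footnote is a permission to treat and not part of the definition; importing it would turn a mandatory stop into discretion, and the confirmation wording would still not match.

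Several stronger readings are tempting, and the documents do not support them:

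- *The SAP assumes nobody is treated past progression.* No SAP passage says so; having no cut-off is equally consistent with treatment continuing.
- *Time to progression is distorted.* Treatment after first progression does not move its date, and SAP Section 10 replaces this endpoint with event-free survival for R/R AML and MDS.
- *DOR fails.* Progression on day 29 and first response on day 57 put into the day formula give 29 − 57 + 1 = −27. But the definition runs from first response to a subsequent event, so an earlier progression cannot end it. The wording merits a clarification and no more.
- *One late response commits the trial to 20 more subjects.* Protocol Sections 3.1.5 and 10.3.2 and SAP 7.1 make this a decision of the Dose Level Review Team on all available data.
- *Responses after progression must be excluded.* That is one convention; the documents do not require it.

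It is also fair that further cycles already need judged benefit, that the interval before the next cycle is set after consulting the sponsor, that the 4-week DLT window is largely untouched by later cycles, that SAP 9.6.9 summarises exposure, and that the protocol calls its efficacy analyses exploratory.

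**Conclusion.** The inconsistency is real and lies in current text. For R/R AML (Groups 1, 4 and 5), Section 6.2.1.5 and the Appendix E footnote cannot both govern the same subject, and Sections 7.2.3 and 8.3.1 add a confirmation condition that is never defined. Following different passages gives different time on treatment, a different adverse event window and a different chance of being counted as a responder.

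The textual conflict needs no assumption. Its numerical effect cannot be estimated: the limits are 0 to 5 further cycles per subject who progresses after cycle 1, in a population of up to about 124. The probabilities shown for the 10-subject review rest on assumed late-response rates. No view is taken here on which treatment rule is right.

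**What to change.** Reconcile Section 6.2.1.5, Section 7.2.3, Section 8.3.1 and the Appendix E footnote into one rule for all sites. Whether it includes a confirmation step or a benefit exception is for the sponsor's clinical team; if confirmation is kept, define it.

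If the reconciled rule allows treatment after progression, add two things to the SAP:

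- Flag and list responses first documented after progression, so that the response rate and the Dose Level Review Team's 10-subject review can be read with and without them.
- State in Section 5.4 that only progression after the first response ends DOR.

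The cost is a wording change in the protocol, for which SAP Section 10 already anticipates Amendment 10, plus a short SAP addition and one extra listing. It needs no extra subjects or assessments unless the sponsor adopts a confirmation step that requires one.

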#### **6.2.2            Marketed Investigational Products – [REDACTED]**

Two marketed products, [REDACTED], will be used prophylactically to mitigate incidence and severity of CRS related to AMG 330 administration. The use of

[REDACTED] for CRS prophylaxis will be investigational in Groups 4 and 5 only and in US only (ie, investigational use of marketed products). Guidance and information on preparation, handling, storage, accountability, destruction, or return of the investigational products, other protocol-required therapies and/or devices during the study are provided in the Investigational Product Instruction Manual (IPIM), a document external to this protocol, and are in accordance with the respective FDA-approved product inserts. Safety information can be found on the [REDACTED] US prescription information document.

[REDACTED] is not FDA-approved for the disease/condition being studied.  
[REDACTED] will be manufactured and packaged by Amgen Inc. and distributed using Amgen clinical study drug distribution procedures. For information on [REDACTED], please refer to the AMG 330 IPIM.

#### 6.2.2.1 [REDACTED]

Only for Groups 4 and 5 (Section 3.1), [REDACTED] will be used prophylactically as a single agent to mitigate incidence/severity of CRS (see Section 3.1.6.1 for guidance on the use of [REDACTED] as a double-agent in combination with dexamethasone). In Group 4, Arm 1, subjects will receive AMG 330 at a dose of [REDACTED] µg/day for [REDACTED] days, [REDACTED] µg/day for [REDACTED] days and [REDACTED] µg/day for [REDACTED] days for a total cycle of [REDACTED] days. [REDACTED] will be administered [REDACTED].

If the best outcome from Group 4 indicates that CRS incidence/severity with [REDACTED] is similar to that observed with dexamethasone premedication alone, then [REDACTED] premedication in combination with an alternative dose step schedule approach will be tested to improve CRS onset dynamics in Group 5. For the mini-step approach, AMG 330 will administered using daily dose steps to reach a target dose of [REDACTED] µg/day.

[REDACTED] will be administered on day [REDACTED] of the study. For the maxi-step approach, a single dose step of AMG 330 at [REDACTED] µg/day will be administered prior to the target dose of [REDACTED] µg/day, and [REDACTED] will be administered on day [REDACTED] of the study.

[REDACTED] can be provided in different marketed presentations including but not limited to [REDACTED]. Additional details regarding this therapy are provided in the IPIM.

#### 6.2.2.2 [REDACTED]

Only for Groups 4 and 5 (Section 3.1), [REDACTED] will be used prophylactically as a single agent to mitigate incidence/severity of CRS (see Section 3.1.6.1 for guidance on the use of [REDACTED] as a double-agent in combination with dexamethasone). For subjects in Group 4, Arm 1, [REDACTED] will be used prophylactically to mitigate incidence/severity of CRS. In Group 4, Arm 2, subjects will receive AMG 330 at a dose of [REDACTED] µg/day for [REDACTED] days, [REDACTED] µg/day for [REDACTED] days and [REDACTED] µg/day for [REDACTED] days for a total cycle of [REDACTED] days. [REDACTED] will be administered IV at a dose of 8mg/kg one hour prior to the initiation of AMG 330 dosing on cycle 1, day 1.

If the best outcome from Group 4 indicates that CRS incidence/severity with [REDACTED] is similar to that observed with dexamethasone premedication alone, then [REDACTED] premedication in combination with an alternative dose step schedule approach will be tested to improve CRS onset dynamics In Group 5. For the mini-step approach, AMG 330 will be administered using daily dose steps to reach a target dose of [REDACTED] µg/day. For the maxi-step approach, a single dose step of AMG 330 at [REDACTED] µg/day will be administered prior to the target dose of [REDACTED] µg/day. [REDACTED] will be administered one hour prior to initiation of AMG 330 dosing during each cycle. Additional details regarding this therapy are provided in the IPIM.

### 6.3 Other Protocol-required Therapies

All other protocol-required and recommended therapies including corticosteroids, that are commercially available are not provided or reimbursed by Amgen (except if required by local regulation). The investigator will be responsible for obtaining supplies of these therapies. Please also refer to Section 6.5.

**Dexamethasone:** Premedication with dexamethasone is required prior to each AMG 330 treatment cycle and prior to each dose step for the prevention of CRS (Exception: see instructions for dexamethasone use in Groups 4 and 5).

Dexamethasone should be administered as a single IV dose (8 mg) within 1 hour of start of infusion or dose step, respectively.

In the case of restart of infusion after an infusion interruption of > 24 hours, dexamethasone (8 mg IV) should be administered within 1 hour prior to restart and within 1 hour prior to the dose step.

For administration of dexamethasone after occurrence of CRS, follow guidance in Section 6.6 below.

## 6.4 Hepatotoxicity Stopping and Rechallenge Rules

Subjects with abnormal hepatic laboratory values (ie, ALP, AST, ALT, total bilirubin [TBL], and/or international normalized ratio [INR]) and/or signs/symptoms of hepatitis (as described below) may meet the criteria for withholding or permanent discontinuation of Amgen investigational product or other protocol-required therapies as specified in the FDA, 2009.

### 6.4.1 Criteria for Permanent Withholding of Amgen Investigational Product due to Potential Hepatotoxicity

Investigational product should be discontinued permanently and the subject should be followed according to the recommendations in [Appendix A](#) (Additional Safety Assessment Information) for possible drug-induced liver injury (DILI), if ALL of the criteria below are met:

ALT or AST > 3.0 ULN; TBL  $\geq$  2.0 ULN or INR > 1.5, ALP < 2.0 ULN; and no other confounding factors including preexisting or acute liver disease (FDA, 2009).

- Important alternative causes for elevated AST/ALT and/or TBL values include, but are not limited to:
  - Hepatobiliary tract disease
  - Viral hepatitis (eg, Hepatitis A/B/C/D/E, Epstein-Barr Virus, cytomegalovirus, Herpes Simplex Virus, Varicella, toxoplasmosis, and Parvovirus)
  - Right sided heart failure, hypotension, or any cause of hypoxia to the liver causing ischemia
  - Exposure to hepatotoxic agents/drugs or hepatotoxins, including herbal and dietary supplements, plants, and mushrooms
  - Heritable disorders causing impaired glucuronidation (eg, Gilbert's Syndrome, Crigler-Najjar syndrome) and drugs that inhibit bilirubin glucuronidation (eg, indinavir, atazanavir)
  - Alpha-one antitrypsin deficiency
  - Alcoholic hepatitis
  - Autoimmune hepatitis
  - Wilson's disease and hemochromatosis
  - Nonalcoholic Fatty Liver Disease including steatohepatitis
  - Non-hepatic causes (eg, rhabdomyolysis, hemolysis)

